- l. Subjects will be asked to collect the first stool of every day in the provided container and to store this in the provided thermal bag with cooling elements: after each vaccine dose, daily collection on Days 0 to 10 plus collection on Days 14, 21, V4 minus 1 or 2 days (= V7 minus 1 or 2 days after 2nd vaccination) and V8 minus 1 or 2 days. At Day 0, the storage procedure will be explained and the collection material provided. Subjects who are still shedding virus in one of the 3 last stool samples will be asked to further collect 3 consecutive stool samples every 3 weeks till end of shedding.
- m. Remote contact (text message by sms, WhatsApp or email) on Day 3 and on Days 21, 31 and 49 for safety follow-up and reminder stool collection scheme.
- n. Adverse events and intake of concomitant medication(s) will be monitored continuously from informed consent until the last study-related activity. The subjects can record unsolicited AEs on their diary card.
- o. After signing on screening visit, weekly reminder Code of Conduct by email or sms and on each visit to emphasize the need and importance of hygienic measures and respecting the inclusion/exclusion criteria until end of study.

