Non-inferiority comparisons will be conducted by computing the difference in endpoint between each candidate vaccine and the UAM1 Sabin 2 control (novel minus comparator), with corresponding two-sided $\alpha = 0.05$ confidence intervals, with inference drawn from comparison of the lower confidence limit to the non-inferiority margin.

Score-based confidence intervals will be used for binary comparisons, asymptotic normal-based methods will be used for GMTs, and bootstrap methods will be used for median titers and other continuous endpoints.

Immunogenicity comparisons will be based on the combined data from each site in this study compared to the single-site data from the historical control study, UAM1. In the event that between-site comparisons within this study indicate that significant differences in outcomes (two-sided tests for differences at $\alpha = 0.05$) exist between sites, additional

comparisons for all immunogenicity endpoints will be added to compare vaccine candidates using only data at the site in common between both studies. Comparisons of binary endpoints between sites in this study will be based on 95% two-sided score intervals for the difference; comparison of continuous endpoints will be based in two-sided 95% bootstrap-based confidence intervals for the difference in medians (median titer), or normal-based methods (for GMTs). Differences between sites will be indicated by a nominal value (percent/median/mean difference of zero) excluded from the confidence interval coverage region.

Viral Shedding

For each group (excluding Group 7), site, and time point, viral shedding positivity and concentration will be summarized. For each subject, a viral shedding index will be calculated as the average of \log_{10} -transformed values of viral concentration in stool samples as determined using quantitative PCR (viral identity) and CCID₅₀ (titer) from select stool samples taken following each vaccine dose, and this index will be summarized by group. The time to cessation of shedding, defined as the time interval between administration of vaccine and the last day of shedding positivity prior to cessation, will be assessed with Kaplan-Meier methods to describe and compare the duration of shedding.

Descriptive analysis and plots of the reverse cumulative distribution of the viral shedding index will be generated.

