6.7 Viral Shedding Analyses

Viral shedding analyses will be descriptive in nature and will include hypothesis tests contrasting nOPV2 recipients with mOPV2 recipients as defined below. The total vaccinated population will be used for viral shedding analyses following the first dose, and the per-protocol population will be used for viral shedding analyses following the 2nd dose. As above, post-dose-1 (pre-dose-2) samples will be combined within vaccine candidate and prior vaccination history, where relevant (combined Groups 1 & 2 for each of UAM1 and UAM4, combined Groups 3 & 4 for UAM4).

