6.7.1 Exploratory Viral Shedding Endpoints

Throughout, viral shedding analyses will be conducted by group and dose number. The descriptive summaries below will also be computed separately by site. Between-group inferential analyses will additionally be conducted among the site in common between UAM1 and UAM4, for OPV-vaccinated subjects, if the post-dose-1 between-site GMT comparison indicates a significant difference in immunogenicity between sites. The shedding analyses will be conducted considering all available samples, collected at Days 0-10, 14, 21, 28, and 42 following each dose (with day of vaccination defined as Day 0) and additional samples collected, as necessary, to define the end of shedding for participants. All viral shedding data will be listed, including both sample collection and assay results.

Categorical summaries of type 2 viral shedding positivity (positive via PCR) and continuous summaries of viral titers (\log_{10} CCID₅₀/g among both shedders and shedders/non-shedders combined) will be produced by group and by post-vaccination day. Each of these will be augmented with two-sided 95% confidence intervals. The Clopper-Pearson exact method will be used for shedding positivity rate, and the bootstrap method (10,000 replicates, quantile method) will be used for the median \log_{10} viral titers. Subjects who are PCR-negative for viral shedding at a given time point will be assigned the value of 0 for computations involving the \log_{10} CCID₅₀/g, and values PCR positive for type 2 poliovirus but below LLOQ ($2.75 \log_{10}$ CCID₅₀/g) or above ULOQ ($8.25 \log_{10}$ CCID₅₀/g) will be assigned the corresponding value of LLOQ or ULOQ.

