For each subject, the extent of viral shedding will be calculated as the area under the curve (using the linear trapezoidal method) of \log_{10} -transformed values of viral concentration in stool samples as determined using quantitative PCR (viral identity) and CCID₅₀ (titer) from samples taken through 28 days following each vaccine dose, and this continuous variable will be summarized. If a subject is missing two consecutive shedding data points among those intended to be tested for this computation due to samples not provided and/or unevaluable samples, the subject will have a missing value. This requirement regarding consecutive missing samples may be relaxed at the analysis stage if sample size for this computation is significantly impacted. Additionally, the Sheding Index Endpoint (SIE) will be computed as the arithmetic mean of \log_{10} CCID₅₀/g obtained from Days 7, 14, 21, and 28. Here, a single missing daily value will lead to a missing

SIE value, although windows of +/- 2 days will be applied to sample availability. If samples are available at both +1 (+2) and -1 (-2), then the mean \log_{10} CCID₅₀/g from these two days will be used for this computation. This will be summarized as a continuous variable using the same methods for daily viral shedding described above.

Additionally, a summary of time-to-shedding-cessation will be prepared using Kaplan-Meier methods. The day of cessation of shedding will be defined as the day of the first sample negative for shedding after which the following two samples are also negative. Summaries will be produced using Kaplan-Meier methods, and will include quartiles and corresponding 95% confidence intervals, as well as the estimated shedding rate at study days 3, 5, 7, 10, 14, 21, and 28 with corresponding 95% confidence intervals. Subjects who are positive for type 2 viral shedding at their last available assessment date with an evaluable stool sample, or who fail to cease shedding prior to a 2nd dose will be right-censored at the last time point they were known to be shedding virus. The time-to-shedding-cessation curves will be displayed graphically, and the comparison of the difference in time to shedding cessation curves between candidate groups in study M4 and corresponding controls subjects from study UAM1 will be conducted by computing the two-sided log-rank p-value.

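### The SAP's shedding-cessation rule needs no earlier positive sample, so negatives before or between periods of shedding can be scored as cessation

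*SAP*

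**What the plan says.** SAP 6.7.1 gives the derivation. Cessation falls on "the day of the first sample negative for shedding after which the following two samples are also negative". The shedding analyses are to be run "considering all available samples, collected at Days 0-10, 14, 21, 28, and 42 following each dose", and time is counted "with day of vaccination defined as Day 0". SAP 6.7 sets the population: "The total vaccinated population will be used for viral shedding analyses following the first dose". After the second dose it is the per-protocol population. Neither is limited to subjects who shed. Subjects positive at their last evaluable sample, or who do not stop before a second dose, "will be right-censored at the last time point they were known to be shedding virus".

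The resulting times feed the Kaplan-Meier quartiles, the shedding estimates at Days 3, 5, 7, 10, 14, 21 and 28, and a two-sided log-rank test of each candidate against UAM1.

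Protocol 10.1.3 describes the same endpoint as "defined as the time interval between administration of vaccine and the last day of shedding positivity prior to cessation". The collection schedule (Protocol 8.1, Groups 2, 4, 5, 6 and 7, footnote l) is "after each vaccine dose, daily collection on Days 0 to 10 plus collection on Days 14, 21, V4 minus 1 or 2 days", so three samples are due by Day 2. SAP Section 7 names only the antibody fold rise as a difference from the protocol.

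**The concern.** Cessation should mark the end of shedding. The rule as written finds the earliest run of three negatives anywhere after vaccination, including a run before the virus first appears in stool. The Day 0 sample is taken on the day of vaccination (the schedule marks the second-dose Day 0 stool as collected before dosing). It will therefore usually be negative in a subject not already shedding, and only Days 1 and 2 need to be negative to complete the run.

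Shedding duration would then be understated for subjects who start late or shed intermittently. If late onset is more common with one vaccine than with the other, the log-rank comparison with UAM1 would be biased in favour of the vaccine with later onset.

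**Working it through.** The plan gives no figure for this endpoint to reproduce. The check applies the rule to example PCR sequences.

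**Inputs.** Sampling days 0-10, 14, 21 and 28, and the event and censoring rules (SAP 6.7.1); the protocol's endpoint (Protocol 10.1.3). The positive days are hypothetical.

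**Rules.** Literal SAP event rule: the smallest day at which that sample and the next two are all negative. Last positive: the last day with a positive sample. Re-anchored rule: the first negative after the last positive, if at least three negatives follow it; otherwise censored at the last positive.

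| Positive on | Literal SAP event rule | Last positive | Re-anchored rule |
|---|---|---|---|
| Days 1-8 | Day 9 | Day 8 | Day 9 |
| Days 2-8 | Day 9 | Day 8 | Day 9 |
| Days 3-8 | Day 0 | Day 8 | Day 9 |
| Days 4-14 | Day 0 | Day 14 | censored Day 14 |
| Days 3-28, still positive | Day 0 (also meets the censoring rule, Day 28) | Day 28 | censored Day 28 |
| Days 1-3 and 7-9 | Day 4 | Day 9 | Day 10 |
| never | Day 0 | undefined | never-positive |

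Moving onset from Day 2 to Day 3 changes the recorded time from Day 9 to Day 0, with the last positive day unchanged. The fifth row meets both the event and the censoring rule, and no precedence is stated. The sixth row is misdated even if an earlier positive is required, because its early gap follows a positive.

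**Dependence on which samples are tested.** If only Days 0, 3, 5, 7, 10, 14, 21 and 28 are tested, the false Day 0 needs Days 0, 3 and 5 all negative. The Days 3-8 subject and the intermittent subject then both get Day 10, and the Days 3-28 subject no longer meets the event rule.

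**Effect on an estimate.** Let *f* be the share of subjects who are negative on Days 0-2, shed past Day 7, and are scored as Day 0 events. With no censoring before Day 7, the Day 7 estimate is

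S_literal(7) = S_true(7) − *f*.

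| Assumed *f* | true 50% becomes | true 30% becomes |
|---|---|---|
| 5% | 45% | 25% |
| 10% | 40% | 20% |
| 20% | 30% | 10% |

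For a candidate against UAM1, the Day 7 difference shifts by −(*f*_candidate − *f*_UAM1). With 10% and 5%, that is −5 percentage points. With equal shares the difference at Day 7 is unshifted, but both curves are too low.

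**The case against.** The strongest reply is that the word cessation implies prior shedding, that the protocol's endpoint needs a positive day, and that a sensible programmer would add the condition. The SAP does not state it. Adding it would still leave intermittent shedders misdated and would require the programmer to invent a time for never-shedders.

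Several stronger inferences do not stand:

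- *That a large, known fraction of shedders is misdated.* If first positivity is assumed uniform on Days 1-3, 1-4 or 2-5, the share with onset on Day 3 or later is 1/3, 2/4 or 3/4. Those values only restate the assumption. On the Day 0/3/5/7/10 subset, with perfect detection and shedding that lasts to the next tested day, all three become zero. The SAP's objectives allow initial testing on that subset, although SAP 6.7.1 speaks of all available samples.
- *That missed stools end shedding early.* An uncollected sample is not a negative sample. Only three consecutive PCR-negative results do this.
- *That the two documents flatly contradict each other.* The protocol measures to the last positive day before cessation but does not define cessation in that section, and the SAP's three negatives match the end-of-shedding criterion in Protocol 9.1. The remaining difference is that the protocol's time ends on a positive day and the SAP's on a negative one that need not follow any positive.
- *That a slow-starting, long-shedding virus must appear to stop earliest.* The censoring sentence also covers subjects positive at their last sample. The SAP does not say which rule wins.

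It is also fair that the endpoint is exploratory and the shedding analyses are described as descriptive. Daily positivity, the area under the curve and the shedding index do not use the rule. Cessation times and censoring flags are listed, so a Day 0 event in a later shedder could be noticed.

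**Conclusion.** The point holds as a defect in a stated rule. Followed as written, it gives a wrong time to late-onset and intermittent shedders and leaves some subjects under two conflicting rules.

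Its size cannot be fixed from the documents, because they give no onset data. It depends on how many subjects have three early or intermittent negatives, and is smaller if only the early-day subset is tested. The loss of *f* percentage points at Day 7 assumes that those subjects are scored as events rather than censored. Bias in the comparison with UAM1 needs the affected share to differ between vaccines.

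This is a should-fix. No primary or secondary endpoint depends on it, so it does not warrant must-fix. It does feed the Kaplan-Meier summaries and an inferential comparison, and correcting it is cheap.

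**What to change.** Replace the definition in SAP 6.7.1 with rules to this effect:

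1. Cessation is the first of at least three consecutive negative samples that follow the subject's last PCR-positive sample in that dose period.
2. Subjects without three such negatives are censored at their last positive sample, and censoring takes precedence over any earlier run of negatives. This also covers a one-dose subject last positive on Day 14 with only two later negatives, whom the present censoring sentence does not reach.
3. Never-positive subjects get time 0 in the all-subject analysis and are also reported separately.
4. For the comparison with UAM1, apply the same rule to both studies over a common window, using samples through about Day 28 of the dose period. UAM1 stool collection ends one or two days before its Day 28 visit (Protocol Appendix 3), while the UAM4 one-dose groups continue to about Day 42 and beyond. Without a common window, late positives could lengthen only the UAM4 times.
5. Reconcile the text with Protocol 10.1.3, or list the change in SAP Section 7.

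One consequence should be stated in the report. With samples on Days 14, 21 and 28 at the end of the window, the last possible run of three negatives starts on Day 14, so no event can fall later. The present three-negative rule has the same limit in that window.

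The cost is one SAP paragraph, a Section 7 entry if needed, and a change to the derivation program. No new data are required.

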The potential risks posed by transmission of the nOPV2 candidate vaccine strains or their genetic variants to an unintended human recipient are estimated by combining the likelihood of transmission with the magnitude of the consequences if transmission occurs. For the groups in which transmission is most likely to occur (close contacts of the study subjects and study site personnel), these consequences are negligible due to previous vaccination, therefore also the overall risk is negligible. The likelihood of transmission to other unintended recipients is considered to be negligible for the general population and low for those in close contact with family members of the study participants. As polio vaccination has been mandatory in Belgium since 1966 and the rate of vaccination of the inhabitants is >95%, practically the entire population is effectively protected from disease caused by the poliovirus, including VAPP. Therefore, the magnitude of the consequences of the nOPV2 candidate vaccine strains or their genetic variants is considered negligible for this group although for those who are unvaccinated or immunocompromised consequences of low magnitude are expected (taking into account the extremely low frequency of occurrence of the serious adverse event of VAPP).

Preliminary data obtained with the candidate nOPV2 vaccines in a first-in-human Phase 1 clinical study in Belgium with IPV-only vaccinated adults (>18 years old) (EudraCT number 2017-000908-21, ClinicalTrials.gov: NCT03430349), confirm that in IPV primed subjects, fecal shedding occurs following administration of the nOPV2 candidate vaccines, with median durations of fecal shedding of about 2 and 4 weeks for the two candidates, yet no nasopharyngeal shedding was observed in this study. This is generally in line with expectations for individuals with an IPV-only vaccination history who are given Sabin OPV.

Presence of vaccine virus in stool was observed somewhat more for vaccine candidate #1 than #2. Some volunteers had more prolonged shedding of vaccine virus in stool, with the longest period for vaccine candidate #1 being almost 3 months and for vaccine candidate #2 just over a month-and-a-half (more detailed data are reported in the IB). None of the volunteers demonstrated any illness associated with longer duration of shedding of vaccine virus.

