- o. After signing on screening visit, weekly reminder Code of Conduct by email or sms and on each visit to emphasize the need and importance of hygienic measures and respecting the inclusion/exclusion criteria until end of study

TIME AND EVENTS SCHEDULE – GROUPS 2, 4, 5, 6, AND 7

Assessments	1	2	3	4	5	6	7	8
Visit	1	2	3	4	5	6	7	8
Time of Visit (days)	D0	D7 (+/- 2D)	D14 (+/- 3D)	D28 (+/- 2D)	D35 (+/- 2D)	D42 (+/- 3D)	D56 ^a (+/- 2D)	D 70 (+/- 4D)
Visit window								
Informed consent ^b	X							
In-/exclusion criteria	X							
Medical history/concomitant diseases	X							
Medication history ^c	X							
Demographic data	X							
Physical examination ^d	X ^e	X	X	X ^e	X	X	X	X
Vital signs ^f	X ^{e,f}	X	X	X ^e	X	X	X	X
Clinical laboratory tests ^g	X ^e	X	X	X ^e	X	X	X	
Pregnancy test ^h	X ^e			X ^e				X
Serology ⁱ	X ^e							
Randomization	X							
Administration of vaccine ^j	X			X				
Serum sample for polio antibodies	X ^e			X ^e			X	
Stool sample for viral culture/quantitative PCR, stool sample for potential poliovirus sequencing, stool sample for potential neurovirulence assay ^l	X-----X ^l	X	X ^e -----X ^l		X	X ^l		X
Solicited systemic AEs (Diary) ^k	X-----X		X-----X					
Remote contact for safety follow-up ^m								
Concomitant therapies ⁿ	X	X	X	X	X	X	X	X
Adverse events ⁿ	X	X	X	X	X	X	X	X
Reminder Code of Conduct	X	X	X	X	X	X	X	X

- a. In case of early termination, the subjects will be asked to return to the clinical site within 14 days after discontinuation for assessments as outlined on Day 56.
- b. No study-related assessment is to be carried out before signing of the informed consent form.
- c. Including polio vaccination history.
- d. Includes weight and height at Day 0. After Day 0, symptom-directed physical examination.
- e. Prior to vaccination.

- f. Blood pressure and heart rate (supine) and oral body temperature. On Day 0 and Day 28, vital signs will be assessed prior to and 30 min after vaccination.
- g. For a list of assessments, please see Appendix 1: Overview of Laboratory assessments.
- h. In women of childbearing potential, a urine pregnancy test will be performed.
- i. Includes HBsAg, anti-HCV and anti-HIV antibodies, and IgA.
- j. The subjects will be kept under medical supervision for at least 30 min after vaccination.
- k. Solicited AEs will be collected for Days 0-7 and Days 28-35.

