3.2 Study design

This is a multicenter, partial blind, placebo-controlled, randomized study in 200 healthy OPV-vaccinated adults and in 48 to 132 healthy IPV-only vaccinated adults (age range 18 to 50 years), as follows:

- 50 OPV-vaccinated adults to receive 1 dose of nOPV2 candidate 1 (Group 1);
- 50 OPV-vaccinated adults to receive 2 doses of nOPV2 candidate 1 (Group 2), administered 28 days apart;
- 50 OPV-vaccinated adults to receive 1 dose of nOPV2 candidate 2 (Group 3);

- 50 OPV-vaccinated adults to receive 2 doses of nOPV2 candidate 2 (Group 4), administered 28 days apart;
- 16 to 44 IPV-only vaccinated adults to receive 2 doses of nOPV2 candidate 1 (Group 5), administered 28 days apart;
- 16 to 44 IPV-only vaccinated adults to receive 2 doses of nOPV2 candidate 2 (Group 6), administered 28 days apart;
- 16 to 44 IPV-only vaccinated adults to receive placebo (Group 7), administered 28 days apart.

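### The three-negative rule, with censoring at the last positive day, informatively censors late stoppers in the two-dose groups, distorting the dose-1 Kaplan-Meier tail and the log-rank test against UAM1

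*SAP*

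**What the plan says.** SAP 6.7.1 defines the cessation day as "the day of the first sample negative for shedding after which the following two samples are also negative". Subjects still positive at their last evaluable stool are right-censored, as are those "who fail to cease shedding prior to a 2nd dose will be right-censored at the last time point they were known to be shedding virus". KM quartiles are reported, with shedding rates up to Days 21 and 28. Candidates are compared with UAM1 by a two-sided log-rank test.

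The stool schedule in Protocol 8.1 is "daily collection on Days 0 to 10 plus collection on Days 14, 21, V4 minus 1 or 2 days", so the third of these late samples falls at about Day 26-27. SAP 6.7.1 describes the samples as "collected at Days 0-10, 14, 21, 28, and 42 following each dose (with day of vaccination defined as Day 0".

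The two-dose schedule in Protocol 8.1 also has a stool entry at the Day 28 visit, carrying the footnote "Prior to vaccination". SAP 6.7 says that "post-dose-1 (pre-dose-2) samples will be combined within vaccine candidate and prior vaccination history". The SAP does not state outright whether the Day 28 pre-dose stool closes the dose-1 series or only opens the dose-2 series.

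Groups 5 and 6 have no one-dose partner; SAP 3.2 lists "16 to 44 IPV-only vaccinated adults to receive 2 doses of nOPV2 candidate 1 (Group 5), administered 28 days apart", and Group 6 likewise for candidate 2. For IPV-primed adults, Protocol 1.3.1 reports phase 1 shedding "with median durations of fecal shedding of about 2 and 4 weeks for the two candidates".

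**The concern.** Kaplan-Meier estimation needs censoring that is unrelated to the event. Here a subject who has just turned negative is removed at the last positive day, because too few stools remain before dose 2 to confirm the change. A subject who is still positive stays in the risk set longer. The estimated curve is therefore too high late in the window, whatever the distribution of durations.

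The late window is where the IPV groups are expected to stop shedding, given phase 1 medians of about 2 and 4 weeks. The report would show a KM rate at Day 28 that disagrees, without explanation, with the daily PCR positivity rate for the same subjects. The OPV comparison has a second problem: the limit on confirming cessation differs between UAM4 and UAM1, so the two arms of the log-rank test are not scored on equal terms.

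**Working it through.** The documents give no expected value for this endpoint, so there is no plan figure to reproduce.

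**1. Latest cessation day that can be scored before dose 2.** After Day 10 the dose-1 stools are Days 14, 21 and about 27, plus Day 28 if the pre-dose stool counts.
- Day 28 not counted: the last possible run of three negatives is Days 14, 21, 27, so the latest event is Day 14. A subject positive on Day 14 and negative on Days 21 and 27 is censored at Day 14.
- Day 28 counted: the last run is Days 21, 27, 28, so the latest event is Day 21. A subject positive on Day 21 and negative on Days 27 and 28 is censored at Day 21.
- One-dose UAM4 groups have a Day 42 stool and extended sampling of late shedders, so they have no such limit before Day 28.

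**2. What KM then estimates in Groups 5 and 6.** With no missing or intermittent samples, nobody is censored before the last scoreable day. KM equals the true survival S up to that day and is flat afterwards: at S(21) if Day 28 counts, at S(14) if not.

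Assumptions: medians of 14 and 28 days (Protocol 1.3.1). Exponential S(t) = 2^(-t/median), or lognormal S(t) = 1 - Φ(ln(t/median)/0.8). The reference for KM at Day 28 is S(27), the last scheduled sample before the Day 28 visit.

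| Case | S(14) | S(21) | S(27) | Counted: excess at Day 28, S(21)-S(27) | Not counted: excess at Day 21, S(14)-S(21) | Not counted: excess at Day 28, S(14)-S(27) |
|---|---|---|---|---|---|---|
| 14 d, exponential | 0.500 | 0.354 | 0.263 | 0.091 | 0.146 | 0.237 |
| 14 d, lognormal | 0.500 | 0.306 | 0.206 | 0.100 | 0.194 | 0.294 |
| 28 d, exponential | 0.707 | 0.595 | 0.513 | 0.082 | 0.112 | 0.195 |
| 28 d, lognormal | 0.807 | 0.640 | 0.518 | 0.122 | 0.166 | 0.289 |

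If Day 28 counts, the excess at Day 21 is zero. A simulation of 200,000 exponential durations gave the same pattern: flat at 0.353 and 0.595 (counted) or 0.498 and 0.707 (not counted). The share censored although the last pre-dose-2 stool was negative was 9-10% (counted) or 19-24% (not counted).

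**3. Scale.** The standard error of a 50% rate is √(0.25/44) = 7.5 points, or √(0.25/16) = 12.5 points. With Day 28 counted, the excess runs from 0.082/0.125 = 0.7 to 0.122/0.075 = 1.6 standard errors.

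**4. Pooled OPV Groups 1+2 and 3+4.** Half of each pool is one-dose.
- Not counted: KM(21) = S(14) × 2S(21)/[S(14)+S(21)], and KM(28) = KM(21) × 2S(27)/[S(21)+S(27)].
- Counted: KM(21) = S(21), and KM(28) = S(21) × 2S(27)/[S(21)+S(27)].

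The documents give no OPV duration. With an assumed exponential median of 7 days, S(14), S(21) and S(27) are 0.250, 0.125 and 0.069.
- Not counted: KM(21) = 0.25 × 0.25/0.375 = 0.167 and KM(28) = 0.167 × 0.138/0.194 = 0.119, excesses of 4 and 5 points.
- Counted: no excess at Day 21, and KM(28) = 0.125 × 0.138/0.194 = 0.089, an excess of 2 points.

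**5. Log-rank test against UAM1.** Protocol Appendix 3 ends UAM1 stool collection at V4 minus 1-2 days for one dose, and at the corresponding V7 sample after dose 2. If UAM1 one-dose subjects without three negatives are also censored at the last positive (the SAP gives no rule for those whose last stool is negative), the UAM1 curve is flat from Day 14. At the 7-day median it stays at 0.25.

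With identical true shedding in both studies, 100 against 100, exponential times and 1,500 runs per case, the nominal 5% test rejected as follows.

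| Assumed OPV median | Day 28 not counted in UAM4 | Day 28 counted in UAM4 |
|---|---|---|
| 5 d | 7% | 8% |
| 7 d | 10% | 16% |
| 10 d | 16% | 27% |
| 14 d | 16% | 33% |

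The mean test statistic favoured faster cessation for the candidates in every case.

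**The case against.** The strongest reply is that the Day 28 stool belongs to dose 1. SAP 6.7 defines the dose-1 set as samples before dose 2, and the schedule marks that stool as taken before vaccination. The Day 0 wording in SAP 6.7.1 can be read as day numbering only. This is the better-supported reading. It removes the Day 21 bias and reduces the rest to one KM time point. It does not remove the informative censoring, and the SAP should not leave the assignment to the programmer.

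Other points also stand. The endpoint is exploratory, and SAP 6.7 calls the shedding analyses descriptive. Three negatives match the study's own end-of-shedding criterion (Protocol 9.1), so relaxing the rule is a trade-off.

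Three stronger inferences are tempting and not supported:
- **That reported dose-1 shedding at Days 21-28 is overstated in general.** Only the KM summary and its log-rank test are affected. Daily PCR positivity, AUC and SIE do not use the rule.
- **That the rule costs the 4-week candidate its median.** At a 28-day true median, survival at the last scheduled dose-1 sample is still 0.513-0.518, so the median sits at the edge of the 28-day window under any rule.
- **That the rule makes the candidates look worse than Sabin 2.** Against the true curve the bias is upward, but UAM1 is affected more, so the formal comparison tilts towards the candidates.

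**Conclusion.** The rule should be changed, although the effect is confined to one exploratory analysis. In Groups 5 and 6 the dose-1 KM curve cannot fall after Day 21, or after Day 14 if the Day 28 stool is not counted. On the better-supported reading, the Day 28 KM rate is about 8-12 points too high and Day 21 is unbiased. On the other reading, the excess is about 11-19 points at Day 21 and 19-29 at Day 28.

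The sizes rest on assumed exponential or lognormal (sigma 0.8) durations, the phase 1 medians, no intermittent shedding and no missing stools. The direction against the true curve does not depend on the distribution.

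For OPV subjects, the log-rank test is biased towards faster cessation for the candidates. The 7-33% rejection range depends on assumed OPV medians of 5-14 days. It also assumes that both UAM1 groups have the Day 14 limit, that is, that UAM1 one-dose subjects are censored like the others and that no Day 28 stool from its two-dose group is used for dose 1.

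**What to change.** Amend SAP 6.7.1 before database lock:
1. State that the pre-dose Day 28 stool is a dose-1 sample.
2. For the post-dose-1 KM, score cessation at the first negative when all later pre-dose-2 stools are negative, or treat it as interval-censored between the last positive and that first negative. Right-censor only subjects positive on their last pre-dose-2 stool.
3. For the log-rank test against UAM1, apply the same rule and one sampling cut (Days 0-10, 14, 21 and V4 minus 1-2 days) to all UAM4 and UAM1 groups. This also covers UAM1 one-dose subjects for whom the SAP has no rule.
4. Keep the three-negative version as a sensitivity analysis.

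No new samples are needed. The cost is SAP wording and reprogramming, which is larger if the interval-censored form replaces the Kaplan-Meier and log-rank methods named in Protocol 10.1.3. Some late cessations will rest on only one or two negatives, so an intermittent shedder may be scored as ceased; the sensitivity analysis shows how much this matters. The comparative test also gives up the one-dose Day 42 and extended data, which remain available for the within-study description.
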